### ***2.5.2 Laboratory Data***

The safety laboratory analysis including chemistry, hematology, urinalysis, coagulation, and CSF safety lab data (CSF WBC, CSF RBC, CSF Protein, CSF Glucose) will be performed at each site's local lab and will be entered on a CRF. These data will be electronically transferred to Ionis Pharmaceuticals, Inc. and stored as SAS data files along with the SAS data files for all other CRFs.

### ***2.5.3 Pharmacokinetics Data***

Ionis Pharmaceuticals, Inc. is responsible for the management and review of the plasma and CSF drug concentration data. Final QA'd data will be stored in Documentum.

## 3 ANALYTICAL PLAN

### 3.1 General Overview of Analyses

#### 3.1.1 *Statistical Methods*

Simple descriptive summary statistics, such as n, mean, standard deviation, standard error, median, interquartile range (25th percentile, 75th percentile), minimum, and maximum for continuous variables, and counts and percentages for categorical variables will be used to summarize most data. Where appropriate, *p*-values will be reported. Null hypotheses will be tested using two-sided tests whose Type I error rates are controlled at alpha = 0.05 unless otherwise stated. Since the primary analysis and secondary analyses are not comparative analysis, adjustments for multiplicity of testing will not be used.

Baseline is defined as the last non-missing value prior to the first dose for ISIS 396443 CS3A.

Age (months) at death or permanent ventilation will be calculated using the following SAS code:

```
yrdif(date1,date2,'ACT/ACT')*12
```

Subject demographic (e.g., age, gender, race, etc.) and baseline characteristics (e.g., age at onset of symptoms, age at SMA diagnosis, SMN2 copy number, subtype of SMA [Type IB if onset of symptoms  $\leq$  2 weeks of age, Type IC if onset of symptoms  $>12$  weeks of age], number of hours of BiPAP support, presence/absence of supplemental G-tube or NG tube feeding within 30 days prior to the first dose, etc.) obtained before the first study drug administration will be summarized by cohort and overall using descriptive statistics.

Subject enrollment and disposition will be summarized. Protocol deviations will be listed.

For by-visit data summary, multiple records with the same visit label will be averaged. Unscheduled results will not be included in the summary tables except for determining baseline, but will be presented in data listings.

The presence/absence of supplemental G-tube or NG tube feeding within 30 days prior to the first dose will be manually reviewed by Ionis physicians.

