**Legend Text *Continued***

- 12 ECG should be performed on Day 568 only
- 13 Immunogenicity assessments will be performed as deemed necessary on samples collected on other days
- 14 All subjects who have maintained a CHOP INTEND total score of  $\geq 50$  for 2 consecutive study visits will be evaluated using the Hammersmith Functional Motor Scale Expanded (HFMSE) in addition to CHOP INTEND

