### **3.6 Safety Analyses**

Safety will be assessed by summarizing the incidence and type of AEs and SAEs. Laboratory parameters will be provided in the data listings.

Days of exposure, number of doses and total amount of drug received for each subject will be summarized by cohort and overall.

Time on study will be categorized into intervals and summarized by cohort and overall.

The time on study will be defined as the total number of days a subject is known to be followed on study calculated as follows:

$$\text{Time on study} = \text{Last date on study} - \text{Date of first dose} + 1.$$

Where the last date on study is defined as the date of the latest visit or evaluation or telephone contact, or time of death from all available data for a given subject.

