Each subject's laboratory values will be classified according to whether the test result is "low" (i.e., below the lower limit of normal [LLN]), "normal" (within the normal range), or "high" (i.e., above the upper limit of normal [ULN]). If a subject is missing a baseline value but had a post-baseline value, then the baseline assessment is labeled as "unknown". Likewise, if a subject had a baseline value but had no post-baseline values, then the minimum and maximum are labeled as "unknown". Post-baseline laboratory results are defined as any assessment taken after the first dose. The shifts (relative to the normal range) from baseline to the minimum and maximum post-baseline values will be presented. Should a treatment affect a laboratory parameter, that parameter could be affected at different times for different subjects. Therefore, these analyses present the most extreme values for each subject. For many laboratory parameters, the effect could be in either direction, (i.e., an increase or a decrease), so both the maximum and minimum values have been analyzed. From these, the shifts (relative to the normal range) from baseline to low and high will be calculated. If a subject's value shifts, it can change from normal to either low or high, from low to normal or high, from high to normal or low, or from unknown to low, normal, or high. For each parameter, the incidence of shift to low will be summarized using the minimum post-baseline values. Shift to low includes subjects with a normal, high, or unknown baseline value and at least one post-baseline value of the given test. Similarly, the incidence of shift to high will be summarized using the maximum post-baseline values. Shift to high includes subjects with a low, normal, or unknown baseline value and at least one post-baseline value.

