### **3.6.5 Lead Electrocardiograms (ECG)**

The ECG data will include ventricular rate (VR), PR interval, QRS duration, QT/QTC, and Overall interpretation.

Outlier analyses will be performed for the corrected Fridericia QT interval (QTcF). This includes summaries of the number and percentage of subjects with a post-baseline QTcF greater than 450 msec, 480 msec, and 500 msec) and the number and percentage of subjects with an increase of 30 msec and 60 msec from baseline in corrected QT interval (QTc). QTcF will be calculated based on the subject's reportable ECG data at each visit using the formula described below:

$$\text{QTcF} = \text{QT} / (\text{RR})^{1/3}, \text{ where RR} = 60/\text{VR}$$

The ECG data will also be provided in a data listing.

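### Taken literally, SAP 3.1.1 drops unscheduled results from the worst-value lab shifts, contradicting SAP 3.6.2, and from the QTcF outlier counts, where nothing overrides it

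*SAP*

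**What the plan says.** **General rule (SAP 3.1.1).** One short paragraph has two sentences. The first is about by-visit tables: "For by-visit data summary, multiple records with the same visit label will be averaged". The second is "Unscheduled results will not be included in the summary tables except for determining baseline, but will be presented in data listings". Its wording is not limited to by-visit tables, and it stands in the general methods section. The same section defines baseline as the last non-missing value before the first dose.

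**Laboratory shifts (SAP 3.6.2).** "Post-baseline laboratory results are defined as any assessment taken after the first dose". Shifts relative to the normal range run from baseline to the post-baseline minimum and maximum. The reason given is that a drug effect may appear at different times in different infants: "Therefore, these analyses present the most extreme values for each subject". The analytes listed include CSF cells, glucose and protein. SAP 3.6 also says "Laboratory parameters will be provided in the data listings", but that does not withdraw the shift tables.

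**QTcF outliers (SAP 3.6.5).** The plan promises "summaries of the number and percentage of subjects with a post-baseline QTcF greater than 450 msec", the same for 480 and 500 msec, and counts of infants with increases of 30 and 60 msec. QTcF comes from the reportable ECG data at each visit. Unscheduled ECGs are not mentioned.

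**Scheduled ECGs (Protocol Appendix A).** After baseline, ECGs are marked on Days 29, 92 and 337. For the group of visits from Day 442 to Day 1198, the legend says "ECG should be performed on Day 568 only".

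**The concern.** A worst-value table is meant to catch an abnormality whenever it occurs. A rule that admits only scheduled results defeats that purpose for any infant whose sole out-of-range value came between visits. Two programmers could follow this SAP faithfully and produce different tables: one filters on 3.1.1, the other keeps everything under 3.6.2.

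Safety and tolerability is a secondary objective, and SAP 3.1.3 says the sample size was chosen so that safety would be adequately assessed. The shift and QTcF tables are the planned incidence summaries for laboratory and ECG data. Protocol 9.5.1 also has clinically significant laboratory abnormalities monitored until they return to baseline or agreement is reached. With safety labs 105 and then 126 days apart after Day 337, some of that follow-up may fall outside scheduled visits.

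**Working it through.** The plan gives no figure on this point, so there is none to reproduce. The check has four parts.

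**1. The rules side by side.**
- Lab shifts: 3.1.1 read literally excludes unscheduled post-dose values; 3.6.2 includes any value after the first dose. This is a direct conflict.
- QTcF outliers: 3.1.1 read literally excludes unscheduled ECGs; 3.6.5 is silent. Nothing overrides the exclusion.

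**2. Direction of the effect.** Let A be all of an infant's post-dose values and S the scheduled ones, with S contained in A. Then max(S) ≤ max(A) and min(S) ≥ min(A). With baseline held fixed, an infant counted under S is always counted under A, but not the reverse. So the count under S is equal to or below the count under A. The percentage follows the count as long as each infant has at least one scheduled post-dose value, so that the denominator does not change.

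Only infants whose scheduled values never meet the criterion are affected. A repeat of a value already out of range in the same direction does not alter a shift count. For QTcF, an infant with every scheduled value at or below 450 msec and one unscheduled value above 500 msec would be missing from all three threshold counts.

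**3. How much the schedule covers (Appendix A).**
- ECG: Days 29, 92, 337 and 568. Gaps from Day 1 are 28, 63, 245 and 231 days. Dosing continues for 1261 − 568 = 693 days after the last of these, covering six of the twelve doses (Days 631, 757, 883, 1009, 1135 and 1261).
- Safety labs: Days 29, 92, 169, 253, 337, 442, 568, 694, 820, 946, 1072 and 1198. Gaps run from 28 to 126 days.
- CSF: pre-dose on 12 injection days. Day 1 precedes the first dose, so 11 are post-baseline.

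As illustration, assume an abnormality lasting L days whose start is uniform over the days that let it finish by Day 1352. There are 1352 − L + 1 possible start days, and the abnormality is missed if no scheduled test day falls within it. For ECG and L = 7, the share caught is 4 × 7 / 1346 = 2.1%, so 97.9% is missed. L is an assumption; the documents give no durations.

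- L = 7: ECG misses 97.9%, labs 93.8%
- L = 14: ECG 95.8%, labs 87.5%
- L = 28: ECG 91.5%, labs 74.6%
- L = 56: ECG 84.8%, labs 50.3%

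The Day 1352 column is not readable in the available Appendix A. Adding a test on that day changes these shares by about 0.1 point. They describe the sparsity of the schedule. They do not estimate lost events, because the rule affects only abnormalities that actually had an unscheduled test.

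**4. Size per infant.** Overall: 1/20 = 5 points. Cohort 1: 1/4 = 25 points. These denominators can move. Planned enrolment is about 8 to 20 (1/8 = 12.5 points), Cohort 1 may grow to 6 (1/6 = 16.7 points), and the shift tables leave out infants already low or already high at baseline.

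**The case against.** The strongest reply is that the exclusion sentence follows directly on one about by-visit summaries and may have been meant for those tables only. For labs, 3.6.2 has its own definition, and a section-specific definition normally governs over a general convention. Both arguments are fair. A reader might infer that unscheduled results are certainly barred from every summary table; the documents do not establish that. What stands is that 3.1.1 does not state the limit, and that 3.6.5 has no definition of its own to fall back on.

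A reader might also infer that the rule always biases towards fewer abnormalities, because the baseline exception works in one direction only. It does not. An unscheduled abnormal pre-dose value can remove an infant from a shift count, but an unscheduled normal repeat after an abnormal screening value can make the infant eligible. A lower unscheduled baseline QTcF makes a 30 or 60 msec increase easier to reach. The one-directional argument covers only the dropping of post-dose values.

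Finally, other routes exist. Unscheduled values stay in the listings, the DSMB reviews safety data throughout, and clinically significant abnormalities may be recorded as adverse events, which are tabulated. These weaken any claim that a safety signal would be hidden. They do not restore the promised counts: adverse event reporting rests on the investigator's opinion, and Protocol 9.5.1 says abnormalities judged not clinically significant should not be reported as adverse events, whereas 3.6.2 counts by normal range whatever that judgement.

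**Conclusion.** The point holds as an unresolved conflict for the laboratory shifts and as an exclusion without an override for the QTcF outlier counts, where it is strongest. If the literal rule is applied, the post-dose counts can only stay the same or fall, given a fixed baseline. The overall size cannot be computed: the documents give neither the number of unscheduled tests nor the reasons for them. The 5-point and 25-point figures are per affected infant and illustrative.

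The documents do not support the firmer statement that the tables will omit abnormal results and understate safety signals. That would require the literal reading to be the intended one, and at least one infant whose only qualifying value was unscheduled. The ECG day list rests on the readable part of Appendix A. A Day 1352 ECG, if scheduled, would not bring back an excluded unscheduled one. The primary efficacy analysis is not at issue.

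**What to change.** - In SAP 3.1.1, state that unscheduled results are excluded from by-visit summaries only, and keep the baseline provision.
- In SAP 3.6.2, state that the minimum and maximum shift tables use all post-first-dose results, scheduled and unscheduled.
- In SAP 3.6.5, state the same for the QTcF threshold and QTcF increase tables.

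The cost is two or three sentences and one programming filter. No new data are needed, since the unscheduled results are already to be listed. The downside is that reported abnormality rates may be slightly higher. If the sponsor does intend scheduled results only, 3.6.2 should be changed to say so, and the tables should not be described as showing each infant's most extreme values.

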#### 3.1.2 *Subject Population Analyzed*

Safety Population will include all subjects who are registered and receive at least one dose of study drug.

Pharmacokinetic (PK) Population will include all subjects who are registered and for which there is at least one evaluable post-dose pharmacokinetic sample. The Efficacy Evaluable (Evaluable) Population will include all subjects who are registered, receive all scheduled

loading doses of study drug (i.e., Days 1, 15 and 85), and complete visits through at least Day 92. Two SMN2 Copy Set will include subset of Evaluable Population who have 2 copies of the *SMN2* gene. Safety analyses will be conducted on the Safety Population, PK analyses will be conducted in PK Population, efficacy and biomarker analyses will be conducted on the Evaluable Population and 2 SMN2 Copy Set. In addition to the Safety Population, PK Population and Evaluable Population, it is recognized that some data displays will be provided for “All Screened”, “All Enrolled”, and “Screening Failures” subjects but no data analysis will be executed in these populations.

### ***3.1.3 Sample Size Consideration***

There is no statistical rationale for the selected sample size for the assessment of efficacy, since no data on the rate of motor milestone response, the primary efficacy endpoint of the study, existed at the time of the study design. The sample size was selected to ensure that the safety, tolerability, and pharmacokinetics of ISIS 396443 will be adequately assessed while minimizing unnecessary subject exposure. According to Table 1, the sample size also allows for sufficient power (~90%) to detect a response rate of at least 30%.

Table 1 below provides the power analysis for 20 patients using the proportion of patients who achieved improvement based on the motor milestone endpoint (as defined in section 1.3.1). A two-sided exact test based on the binomial probability distribution with an alpha of 0.05 is used.

**Table 1. Power analysis for 20 patients using the proportion of patients who achieved improvement based on the motor milestone**

Null hypothesis, $H_0$	Alternative hypothesis, $H_a$	Power
5% (1 responder)	20% (4 responders)	58%
5%	25% (5 responders)	77%
5%	30% (6 responders)	89%
5%	35% (7 responders)	95%

### ***3.1.4 Safety Review and Planned Interim Analysis***

To ensure subject safety, safety data will be reviewed on an ongoing basis by the Ionis Safety Physician. Safety data will also be reviewed on an ongoing basis by the Data and Safety Monitoring Board (DSMB). After the last patient within Cohort 1 completes the Day 29 visit, safety results for the cohort will be reviewed by the Medical Monitor and the DSMB and a recommendation regarding further enrollment and escalation to Cohort 2 will be made. The Sponsor and DSMB will determine if enrollment of additional patients is required to confirm there is an acceptable toxicity profile prior to its designation as MTD.

Interim efficacy and safety analyses will be performed to provide content for regulatory submissions and to support ISIS 396443 drug development planning and business activities. Specifically, analyses of primary and secondary efficacy endpoints (Sections 3.2 and 3.3), as well as PK (Section 3.5) and safety analyses (Section 3.6), will be conducted at time points that allow for reasonable interpretation of the data, such as all continuing subjects passing a specific age threshold (e.g., 18, 24 or 36 months).

### ***3.1.5 Incomplete or Missing Data***

#### ***3.1.5.1 Motor Milestones***

If not all tests were performed at a visit, the approach described below will be used for the handling of missing data. Missing data will be imputed on an individual item level. If a test is missing at screening, then the missing test will be imputed as the median of the non-missing values of the group to which the subject belongs: age at symptom onset ( $\leq 2$  weeks,  $>12$  weeks) by disease duration ( $\leq 2$  weeks,  $>12$  weeks). If for the subject with the missing test, the corresponding visit is flanked by visits with non-missing tests, the missing test will be imputed using linear interpolation with the result rounded to the nearest integer score. Otherwise, the missing test will be imputed as the lowest score of the visit in the group (age at symptom onset by disease duration) to which the subject belongs. If the group is empty, the missing test will be imputed as the lowest score of all available subjects of the visit.

Disease duration (week) will be calculated as (screening date-birth date)/7- age at symptom onset in week.

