## **Appendix A – Schedule of Procedures for ‘Loading’ Dosing Period, Visits Only\* *Continued***

### **Legend Text *Continued***

- 8 CMAP and CHOP INTEND assessments do not form part of the screening assessment or inclusion/exclusion criteria but are baseline measurements taken during the screening phase of the study
- 9 Overnight stay is optional on Day 15 and Day 85, if needed due to complications of the LP procedure
- 10 Injections may not be scheduled within 72 hours after an immunization
- 11 Refer to Appendix C for PK sampling schedule
- 12 Refer to Appendix B for analytes
- 13 At telephone contact, changes in concomitant medications and adverse events will be recorded as well as information on the subject's ventilator use and SMA disease status

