#### ***3.1.5.2 CHOP-INTEND Total Score***

The CHOP-INTEND assessment contains 16 items, 13 of them are tested on both right side and left side. The item score will be equal to the maximum score of both sides for those 13 items. If the score for one side is missing the item score will be equal to the score of the non-missing side.

If not all tests were performed at a visit, the approach described below will be used for the handling of missing data. Missing data will be imputed on an individual item level. If a test is missing at screening, then the missing test will be imputed as the median of the non-missing values of the group to which the subject belongs: age at symptom onset ( $\leq 2$  weeks,  $>12$  weeks) by disease duration ( $\leq 2$  weeks,  $>12$  weeks). If for the subject with the missing test, the corresponding visit is flanked by visits with non-missing tests, the missing test will be imputed using linear interpolation with the result rounded to the nearest integer score. Otherwise, the missing test will be imputed as the lowest score of the visit in the group (age at symptom onset by disease duration) to which the subject belongs. If the group is empty, the missing test will be imputed as the lowest score of all available subjects of the visit.

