## 3.2 Primary Efficacy Analysis

Motor milestones will be assessed using Section 2 of the Hammersmith Infant Neurological Exam (HINE) which is comprised of eight independent milestone categories: voluntary grasp, ability to kick in supine position, head control, rolling, sitting, crawling, standing, and walking. Within each of these categories, subjects can progress from complete inability to perform a motor task, for example no grasp, no kicking, unable to maintain head upright, all the way to complete mastery of each category, for example achievement of pincer grasp, touching toes while supine, maintaining their head upright for a maximum of 26 motor milestones (see Table 2 below).

Table 2. Motor Milestone Achievement (Module 2, HINE)

Motor milestone	Milestone progression				
	No grasp	Uses whole hand	Finger and thumb; immature grasp	Pincer grasp	→
Voluntary grasp					
Ability to kick (in supine)	No kicking	Kicks horizontal; legs do not lift	Upward (vertically)	Touches leg	Touches toes
Head control	Unable to maintain upright	Wobbles	All the time upright		
Rolling	No rolling	Rolling to side	Prone to supine	Supine to prone	
Sitting	Cannot sit	Sit with support at hips	Props	Stable sit	Pivots (rotates)
Crawling	Does not lift head	On elbow	On outstretched hand	Crawling flat on abdomen	On hands and knees
Standing	Does not support weight	Supports weight	Stands support	with	Stands unaided
Walking	No walking	Bouncing	Cruising (holding on)	Walking independently	

For each dosing visit, in addition to the scheduled pre-dose assessment, the HINE including motor milestones are also assessed at 3, 6 hours and 1 day after dosing to monitor patient safety. Since the patient's motor function could be temporarily impacted by the lumbar puncture procedure, only the motor milestone results from the pre-dose assessment will be

used for the efficacy analysis and the results at 3, 6 hours and 1 day after dosing will be excluded.

The improvement in motor milestones is defined as achievement of any of the following :

- (i) at least a 2-point increase from baseline or achievement of pincer grasp in the category of voluntary grasp, or
- (ii) at least a 2-point increase in the ability to kick or achievement of touching toes, or
- (iii) a 1-point increase in any of the remaining 6 categories: head control, rolling, sitting, crawling, standing, or walking.

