Subjects who die or withdraw from the study will be counted as non-responders and will be included in the denominator for the calculation of the proportion. As a result, mortality will be accounted for in the motor milestone analysis. For subjects on permanent ventilation, because motor milestone assessment continues, functional scores after permanent ventilation will be used to assess improvement in motor milestones.

The primary analysis will be the proportion of subjects who achieve improvement in motor milestones at their last available visit. It will be tabulated by cohort and overall. The primary analysis will be conducted using the Evaluable Population.

As the sensitivity analyses, the proportion of subjects who achieve improvement in motor milestones at their last available visit will be tabulated

- 1). by cohort and overall using the 2 SMN2 Copy Set
- 2). by cohort and overall using the Safety Population
- 3). by SMA subtype using the Safety Population

In addition, the following analyses will also be conducted to assess effects of treatment with ISIS 396443 on the motor milestone improvement over time:

- The proportion of subjects who achieve improvement in motor milestones will be tabulated by visit.

Subjects who die or withdraw from the study prior to a visit will be counted as non-responders for the visit and all subsequent visits and will be included in the denominator for the calculation of the proportion. As a result, mortality will be accounted for in the motor milestone analysis. For subjects on permanent ventilation, because motor milestone assessment continues, functional scores after permanent ventilation will be used to assess improvement in motor milestones.

If a subject misses a visit and has visit(s) beyond the visit, then the subject will be counted as a non-responder and included in the denominator for the calculation of the proportion for the visit.

Subjects who are ongoing in the study and haven't reached a visit will not be included in the denominator for the calculation of the proportion for the visit and all subsequent visits.

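### A motor milestone item missing at a partly completed last visit takes other infants' lowest score with no cap at the infant's own, so imputation alone can create a primary-endpoint responder

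*SAP*

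**What the plan says.** SAP 3.1.5.1 imputes item by item when an attended visit is only partly completed. After screening there are two routes. If the infant has the item at visits on both sides, the value is interpolated linearly and rounded. In all other cases: "Otherwise, the missing test will be imputed as the lowest score of the visit in the group". Groups are formed by age at symptom onset and disease duration. SAP 3.1.5.2 repeats the rule for CHOP INTEND, and both sections close with the same fallback: "If the group is empty, the missing test will be imputed as the lowest score of all available subjects of the visit".

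SAP 3.2 fixes the time point: "The primary analysis will be the proportion of subjects who achieve improvement in motor milestones at their last available visit". Infants who have died or withdrawn are non-responders and stay in the denominator. Response needs only one of several criteria; for head control, rolling, sitting, crawling, standing and walking the criterion is "a 1-point increase in any of the remaining 6 categories".

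For the by-visit tables, SAP 3.2 treats a wholly missed visit differently: "If a subject misses a visit and has visit(s) beyond the visit, then the subject will be counted as a non-responder".

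**The concern.** Taking the lowest score looks conservative, and was presumably meant to be. But it is the lowest score of other children. It is conservative for this infant only if at least one of them scores no higher than this infant's own level. The infant's baseline and last observed score do not enter the rule.

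The last available visit is where this matters most, because interpolation between the infant's own scores is impossible there. It is also where few infants may contribute. Those who died, withdrew or have not reached the visit supply no score, and SAP 3.1.4 plans interim analyses at points "such as all continuing subjects passing a specific age threshold". Removing members from a group can leave its minimum unchanged or raise it, never lower it.

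At stake is a single proportion in about 20 infants, in which one responder based on an unobserved item would be visible. The by-visit rule for a missed visit gives no credit without an observation; the item rule at an attended visit can.

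**Working it through.** **1. Which rule applies.** Interpolation needs a later visit with the item. The last available visit has none. A missing item there is therefore always set to the group minimum or, if no group member has a score, to the minimum over all available subjects.

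**2. Can this create a responder?** Take an infant with head control 0 at baseline and at the last observation, the item missing at the last visit, and no response on any observed item. The rule gives imputed score = min(scores of the others). The infant is a responder if imputed score − baseline ≥ 1. The capped score is min(imputed score, own last observed score).

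| Others' scores at that visit | Imputed | Responder? | Capped at own last score (0) | Responder? |
|---|---|---|---|---|
| group: 1 | 1 | yes | 0 | no |
| group: 1, 2 | 1 | yes | 0 | no |
| group: 1, 2, 1, 2 | 1 | yes | 0 | no |
| group: 0, 1, 2 | 0 | no | 0 | no |
| group empty; all subjects: 1, 2, 1 | 1 | yes | 0 | no |
| group empty; all subjects: 0, 1, 2 | 0 | no | 0 | no |

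So it can, provided every contributing infant scores above this infant's baseline. One low scorer blocks it. With one other group member, that child's score is simply copied.

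**3. Can the rule work the other way?** Take baseline 0, a gain to 1 that the infant still has, the item missing at the last visit, and group scores 0, 1, 2. The imputed score is 0. If this was the infant's only gain, a true responder is lost. The cap gives min(0, 1) = 0 and does not restore it.

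**4. What the cap leaves open.** Take baseline 0, last observed score 1, a skill lost since but not tested at the last visit, and group scores 1, 2. The uncapped score is 1 and the capped score is min(1, 1) = 1. The observed gain is carried forward although it has gone.

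**5. Size.** One infant is 1/20 = 5 percentage points overall. In the by-cohort table, with Cohort 1 at its planned 4, it is 1/4 = 25 points.

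SAP 3.1.3 supplies a benchmark with 20 infants and a 5% null: "A two-sided exact test based on the binomial probability distribution with an alpha of 0.05 is used". Its power figures reproduce. With X binomial (20, 0.05), P(X ≥ 3) = 0.0755 and P(X ≥ 4) = 0.0159. Against 0.025 in the upper tail, rejection needs 4 responders. P(X ≥ 4) at true rates of 20, 25, 30 and 35% is 58.9, 77.5, 89.3 and 95.6%; Table 1 prints 58, 77, 89 and 95%. On that benchmark 3 responders do not reject and 4 do, a difference of one infant. The cap leaves Table 1 unchanged.

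**6. CHOP INTEND.** Response in SAP 3.3.2 needs a gain of at least four points in the total score. Imputed items must supply that gain or complete it on top of observed gains, so the route is weaker.

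**The case against.** The strongest reply is that the case is narrow and the rule usually severe. It needs an attended last visit with an item not done, an infant neither dead nor withdrawn, no response on any observed item, and no contributing infant at or below this infant's baseline on the missing item. In a group of ordinary size one low scorer is enough to block it. An infant alone in a group is compared with all available subjects, which is usually harder to pass. All of that stands, and it is why this is a small improvement and not a threat to the trial.

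A reader might go further in three ways that the documents do not support.

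- **That the rule favours the drug.** Step 3 shows that it can also erase a real responder. Without item-level data the net direction cannot be known.
- **That the chance of a false responder follows from the share of peers scoring above the infant, raised to the number of peers.** That is at best the chance that the minimum on one item exceeds the infant's score. It ignores whether the infant has already responded on another item, and where peers score well that may be common.
- **That the contrast of 3 with 4 responders means a wrong test result.** SAP 3.2 plans a tabulation of the primary proportion, and SAP 3.1.1 calls the primary and secondary analyses non-comparative. The contrast shows scale only.

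**Conclusion.** The gap is real and follows from the text: at a partly completed last available visit, the last-resort rule can credit an infant with a milestone score above anything observed in that infant, and one point in one of six categories is then enough for response. The size is 5 percentage points per infant at 20 infants. It is most plausible where only a few other infants contribute a score.

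This rests on a literal reading of SAP 3.1.5.1 and on at least one item being missing at such a visit. The documents give neither the missing-item rate nor the number contributing in each group, and the rate may be zero. This is an absent limit at the infant's own score, not demonstrated inflation of the response rate. It is a cheap improvement.

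**What to change.** In SAP 3.1.5.1 and 3.1.5.2, impute a post-screening item that cannot be interpolated as the smaller of:

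- (a) the group minimum at that visit, or the minimum over all available subjects if the group is empty; and
- (b) the infant's own last observed score on that item.

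Report how many items were imputed at the last available visit and how many responders depend on an imputed item.

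Last-resort imputation then cannot credit a score above the infant's own last observation. It can still carry forward an observed gain that was later lost, and it does not restore a true gain erased by a low group minimum; the reported counts let a reader judge both.

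The cost is one reworded sentence in each of two sections, one programming line and a short count, with no new data. The downside is a possibly slightly lower response rate, because an infant who gained an item after the last observation and was not tested on it at the last visit gets no credit.
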